7.3 Vital Signs

Vital signs will include pulse rate, respiratory rate, body temperature, and systolic and diastolic blood pressure (average of 3 readings will be taken in a resting state) at the visits indicated in [Table 5–1](#).

7.4 Electrocardiograms

Standard 12-lead ECG assessments will be performed at visits indicated in [Table 5–1](#).

7.5 Concomitant Medication Use

During the study, treatment for the progression of NPDR may be required in the study eye for some subjects as a result of AEs or lack of efficacy of the study treatment. Intervention per the clinical sites standard of care are permitted ([Section 6.6.4](#)). Prohibited medications ([Section 6.6.3](#)), although discouraged, can be used if necessary (eg, no other alternative) but will be considered protocol deviations. Information regarding concomitant medication use will be collected at the visits specified in [Table 5–1](#).

8 REPORTING OF TECHNICAL PRODUCT COMPLAINTS

A Product Complaint (PC) is defined as any written, electronic, or verbal expression of dissatisfaction regarding the identity, quality, reliability, safety, purity, potency, effectiveness, or performance of an investigational or commercial product after it is released for distribution (eg, any failure of the applicator to deliver the intravitreal insert), or dissatisfaction with any other characteristic(s) of the drug product (eg, labeling, packaging, etc.).

Any/all PCs should be reported to EyePoint within 24 hours using the designated PC Report Form. The complaint report should include the following information:

- Product identification number
- Investigator name, study site name, and contact phone number
- Date the complaint occurred
- Brief description of the complaint
- Subject involved? (yes or no); if yes, were any AEs associated with the complaint? (yes or no). If (yes) an AE is associated with the complaint, please refer to [Section 7.1](#)

Once all information is collected please report to:

PPD [REDACTED]
[REDACTED]

The drug container (applicator, foil pouch, and carton) for which the complaint was initiated should be retained for return to EyePoint for analysis.

PPD [REDACTED]
[REDACTED]
[REDACTED]
[REDACTED]

Any complaint about an investigational product must be reported regardless of whether the defect or deficiency had any effect on a subject or on study personnel.

9 PHARMACOKINETICS

Secondary endpoints in this study include the evaluation of the systemic exposure to vorolanib and X-297, its main metabolite, as measured through plasma. Blood samples will be collected at the visits noted in [Table 5–1](#) for PK analysis of vorolanib and its main metabolite concentrations. Collection, handling, storage, and shipment of samples to the designated analytical testing laboratory will be conducted according to the procedures described in [Appendix 3](#).

In the event the subject requires vitrectomy during the study, the unmasked Investigator or designee will collect a vitreous sample and EYP-1901 implants (if applicable) to be sent to sponsor as described in [Appendix 3](#).

10 ASSESSMENT OF EFFICACY

The primary objective of this study is to assess the efficacy of EYP-1901 compared to sham treatment in the improvement of moderately severe to severe NPDR. The primary endpoint of this study will be the percentage of subjects improving ≥ 2 steps from baseline in the DRSS score at Week 36 in each EYP-1901 dose level versus the sham IVT injection group in the study eye.

The DRSS may be used to describe overall retinopathy severity as well as the change in severity over time. Severity ranges from level 10 (DR absent) to level 85 (advanced proliferative DR: posterior fundus obscured, or center of macula detached). Here, DRSS describes severity level 47 (moderately severe NPDR) and level 53 (severe NPDR) at Week 36 from baseline.

Additional secondary endpoints include the following in the study eye (unless otherwise specified):

- Percentage of subjects improving ≥ 2 steps from baseline in the DRSS score at Weeks 24 and 48 in each dose level vs. sham.
- Percentage of subjects improving ≥ 2 -steps or ≥ 3 -steps over time in DRSS from baseline.
- Percentage of subjects worsening ≥ 2 -steps or ≥ 3 -steps over time in DRSS from baseline.

- Percentage of subjects who developed a vision-threatening complication due to diabetic retinopathy at Weeks 24, 36, and 48.
- Percentage of subjects who developed CI-DME at Weeks 24, 36, and 48.
- Time to develop of any neovascular vision threatening complication (PDR/ASNV) through Weeks 24, 36 and 48.
- Time to develop CI-DME through Weeks 24, 36, and 48.
- Percentage of subjects who received anti-VEGF or additional standard of care intervention due to ocular diabetic complications at Weeks 24, 36, and 48.
- Percentage of subjects who received PRP, inclusive of subjects undergoing vitrectomy with endolaser, at Weeks 24, 36. and 48.
- Area under the curve (AUC) for change from baseline in BCVA at Weeks 24, 36, and 48.
- Systemic exposures to vorolanib and X-297, its main metabolite, measured through plasma levels up to Weeks 24 and 48.
- Rates of ocular (study eye and fellow eye) and non-ocular TEAEs at Weeks 24 and 48.

11 STATISTICAL METHODS AND DATA ANALYSIS

Detailed methodology for statistical analyses of the data collected in this study will be documented in a Statistical Analysis Plan (SAP), which will be developed and maintained by the Sponsor.

The SAP may modify the plans outlined in the protocol; however, any major modifications of the primary endpoint definition and/or its analysis will also be reflected in a protocol amendment.

All study data will be presented in by-subject listings.

11.1 Determination of Sample Size

The objectives of the study are to provide efficacy and safety data in a prospective, randomized, double-masked, controlled trial. However, the study is not formally powered to perform statistical hypothesis testing between each EYP-1901 arm versus sham IVT injection.

Approximately 60 subjects will be randomized at 1:1:1 ratio to each of three treatment arms (20 per treatment arm).

11.2 Analysis Population

The intent-to-treat (ITT) population will include all subjects who received at least one dose of study treatment (EYP-1901 or sham). The safety summaries will be based on the ITT population. The subjects will be summarized based on the treatments that they actually receive.

The efficacy population will include all subjects who received at least one dose of study treatment (EYP-1901 or sham) and continue until at least Week 36 (ie, have had the primary endpoint assessed).

11.3 General Statistical Considerations

11.3.1 Data Summarization

Data summaries for variables measured on a continuous scale will include descriptive statistics (n, mean, median, standard deviation, minimum, and maximum) by treatment arm. Data will be pooled for all study sites for data analysis, unless otherwise specified.

For variables evaluated on a categorical scale, data summaries will include the number and percentage of subjects who provide each possible category, by treatment arm. The 95% confidence interval (CI) of the proportions will be constructed, as appropriate.

11.3.2 Definition of Baseline

Baseline measurements are those taken at Screening or prior to receiving study drug on Day 1, whichever is the latest.

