4.1 Inclusion Criteria

Subjects will be considered eligible for participation in the study if all of the following inclusion criteria are satisfied:

1. Men or women ≥ 18 years of age with type 1 or 2 diabetes mellitus. Participants must have a HbA1c $\leq 12\%$ (as confirmed by laboratory assessments obtained at the Screening Visit or by a documented laboratory report dated within 60 days prior to the Screening Visit).
2. Study eye with moderately severe to severe NPDR (based on the DRSS levels 47 or 53), using standard 4-widefield digital stereoscopic fundus photographs confirmed by the CRC, in whom PRP and anti-VEGF injections can be safely deferred for at least 6 months per the Investigator.
3. Best corrected visual acuity (BCVA) using Early Treatment Diabetic Retinopathy Study (ETDRS) letter score in the study eye of ≥ 69 letters (approximate Snellen equivalent of 20/40 or better).
4. Able to understand, and willingness to sign, the informed consent and to provide access to personal health information via Health Insurance Portability and Accountability Act (HIPAA) authorization.
5. Willingness and ability to comply with all scheduled visits, restrictions, and assessments.
6. For women of childbearing potential, or men with female partners of childbearing potential, agreement to the use of an appropriate form of contraception for the duration of the study.

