5 STUDY PROCEDURES

To ensure the health of both eyes, observations of both the study eye and non-study (fellow) eye should be made at all visits as described in the Schedule of Study Procedures and Assessments ([Table 5-1](#)) unless otherwise indicated.

BCVA by ETDRS: The equipment and procedures necessary for testing BCVA are presented in [Appendix 1](#). Visual acuity is always tested with the subject's best correction and should be measured prior to pupil dilation and slit lamp biomicroscopy examination or any drops or ointments are used. BCVA by ETDRS will be measured at every study visit ([Table 5-1](#)). Visual acuity testing in this study is required at a distance of 4 meters, and for subjects with reduced vision at 1 meter. Each site should have at least one certified refractionist available for the use of ETDRS charts. **An ETDRS-certified refractionist** should perform all protocol refraction and BCVA measurements required by the protocol.

Slit lamp Biomicroscopy: Anterior chamber evaluation will be conducted using a slit beam of 1 mm height and 1 mm width with maximum luminance through the highest powered lens using the Investigator's standard slit lamp equipment and procedure. This procedure will be the same for all subjects observed at the Investigator's site. Ocular signs assessments, including vitreous haze, the presence of anterior chamber cells, and will be scored according to the scales and conventions presented in [Appendix 2](#). Ocular examinations will be done at the study visits noted in ([Table 5-1](#)).

Dilated Ophthalmoscopy: Will be performed according to the Investigator's preferred procedure. This procedure will be the same for all subjects observed at the Investigator's site ([Appendix 2](#)). Ocular examinations will be done at the study visits noted in ([Table 5–1](#)).

Intraocular Pressure/Tonometry: IOP will be measured as described in [Appendix 2](#) at the study visits noted in ([Table 5–1](#)).

Wide-Field Fluorescein Angiography and Color Fundus Photography: A study-certified photographer will take mydriatic stereoscopic color photographs and a fluorescein angiogram of both eyes according to the standardized procedures described in the Study Manual. Photography must be performed after testing visual acuity if these procedures are performed on the same day. FA/CFP will be done at the study visits noted in ([Table 5–1](#)).

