### 8.2. Key Definitions

Baseline measurements are defined as the last non-missing measure prior to the initiation of study treatment, likely assessed at Screening or Day 1, but available unscheduled assessments will also be considered.

Study Day 1 will be the date on which study treatment is administered. Positive study days will be counted forward from Study Day 1, and negative study days will be counted backward from Study Day 1, beginning with Study Day -1. There will be no Study Day 0.

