### 9.3. Demographic and Baseline Characteristics

Demographics and baseline characteristics will be summarized for the FAS by treatment arm and overall. The following demographic variables will be listed and summarized:

- Age in years at screening
  - <40 years; 40 to <65 years; ≥65 years

Age in years at screening will be computed using SAS code similar to the following:

`floor(YRDIF(<date of birth variable>, screen date, "AGE"))`

- Sex (Male, Female)

This document is confidential.

- Child-bearing potential (Yes, No). If child bearing potential is "No", then reason will be summarized (surgically sterile, post-menopausal, other)
- Ethnicity (Hispanic or Latino, Not Hispanic or Latino)
- Race (Asian, Black, White, American Indian or Alaska Native, Native Hawaiian or Other Pacific Islander, Other, Unknown)
- Study Eye (OD, OS)

The following baseline characteristics will be listed and summarized:

- Baseline DRSS score in the study eye (43, moderate NPDR; 47, moderately severe NPDR; 53, severe NPDR)
- Baseline DRSS score in the study eye, categorical ( $\leq 47$ ,  $\geq 53$ )
- Baseline HbA1c
  - $\leq 8\%$ ;  $> 8\%$
- Diabetes diagnosis to randomization (years)
- Baseline BCVA ETDRS letter score in the study eye
  - $\leq 55$  letters; 56 – 70 letters;  $\geq 71$  letters
- Baseline CST in the study eye
  - $\leq 300 \mu\text{m}$ ;  $> 300 \mu\text{m}$
- Number of anti-VEGF injections in the study eye prior to screening
  - 0 injections; 1 to 4 injections
- Time since diagnosis of NPDR in years at Screening in the study eye
  - Medical history terms, mapped and/or reported verbatim terms, will be examined by masked team members to identify those indicating NPDR, and the identified list will be logged in the programming specifications. The start date of earliest occurrence from amongst the identified events will be the NPDR diagnosis date and the time since diagnosis at screening will be calculated as screening date minus NPDR diagnosis date, plus 1. If the NPDR diagnosis date is missing only the day, the day will be set to 1, and if the NPDR diagnosis date is missing month and day (but not year), the month and day will be set to January 1.

Summaries will be using both categorical and continuous descriptive statistics, as detailed in [Section 8.1](#). Unless otherwise specified, percentages will be calculated based on the n in the respective population.

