#### Area Under the Curve Endpoint

Observed BCVA values, change from baseline to each follow-up visit, and area under the curve (AUC) for change from baseline in BCVA through Week 24, Week 36, and Week 48 will be summarized descriptively. AUC through each time point of interest will be computed using the trapezoidal rule normalized to months, with a final unit of letters. Mean AUC for change from baseline in BCVA through Week 24, Week 36, and Week 48 will be compared between each active treatment arm and sham IVT using analysis of covariance (ANCOVA) with treatment arm as the main effect and baseline BCVA as a covariate. A plot of mean change from baseline in BCVA score over time will be prepared for the FAS.

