**Table 6: Mapping of DRSS Scores to Numeric Steps**

DRSS Score	Coded Numeric Step
10	0
20	1
35	2
43	3
47	4
53	5
61	6
65	7
71	8
75	9
85	10

The coded numeric values represent whole steps on the DRSS, where Step 0 is no diabetic retinopathy and Step 10 is advanced proliferative diabetic retinopathy. Baseline is defined as the last non-missing DRSS measurement prior to the initiation of study treatment. Change from baseline is computed as follow-up step minus baseline step; a negative change indicates improvement in disease and a positive change indicates worsening of disease.

Observed values and change from baseline will be summarized descriptively by treatment group for the full analysis set.

The SAS MIXED procedure (MMRM) will be used with the REPEATED statement for visits with an unstructured covariance structure and a RANDOM statement set at the subject level. The model will include change from baseline at each visit as the dependent variable and fixed effects for treatment and visit and the interaction between treatment and visit, and baseline DRSS step as a covariate. The Kenward-Roger approximation will be used to estimate denominator degrees of freedom. If there is a convergence issue (lack of convergence in general, or convergence with a non-positive definite estimated

This document is confidential.

G-matrix or non-positive definite Hessian matrix) with the unstructured covariance structure, a Toeplitz or Autoregressive (1) [AR(1)] covariance structure will be used, following this sequence, until convergence is achieved. If the model still does not converge, no results will be reported. Model-based point estimates (i.e., least squares means and least squares mean differences, 80%, 85%, 90%, 95%, and 97.5% CI, and p-values) will be reported at each visit.

This document is confidential.

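### The BCVA AUC ANCOVA adjusts only for the last pre-dose reading; adding Screening BCVA as a second covariate would give somewhat tighter intervals at almost no cost

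*Protocol*

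**What the plan says.** **Baseline.** Protocol 11.3.2 takes one value: "Baseline measurements are those taken at Screening or prior to receiving study drug on Day 1, whichever is the latest". SAP 8.2 restates it: "Baseline measurements are defined as the last non-missing measure prior to the initiation of study treatment", and lets unscheduled pre-dose assessments count.

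**Readings available.** Protocol section 5 states that "BCVA by ETDRS will be measured at every study visit". The schedules (Protocol Table 5-1, SAP Table 1) mark BCVA at both Screening and Day 1. Protocol 3.4 puts 5 to 30 days between the two, and Protocol 3.2 places randomization on Day 1. A study-eye score of at least 69 letters is an inclusion criterion (Protocol 4.1).

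**Model.** Protocol 11.3.5 plans no covariate adjustment. SAP 8.8 and 14 change this for secondary efficacy endpoints, adding the baseline value where applicable. For mean BCVA AUC through Weeks 24, 36 and 48, SAP 10.2 specifies "analysis of covariance (ANCOVA) with treatment arm as the main effect and baseline BCVA as a covariate". No other covariate is named.

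**Size of study.** About 60 subjects, 20 per arm, not formally powered (Protocol 11.1, SAP 4.3).

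**The concern.** A single visual acuity score is the subject's true acuity plus measurement error. When that score is the only covariate, the model removes only part of the between-subject variation in true acuity, and the rest stays in the residual. A second pre-randomization reading of the same quantity lets the model remove more of it.

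The SAP has deliberately added covariate adjustment and an explicit comparison with sham for this endpoint. In an unpowered study with 20 per arm, interval width is the main product of that comparison. Screening BCVA is already collected and, being an entry criterion, should be present for essentially every treated subject.

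**Working it through.** **No plan figure to reproduce.** The documents give no precision target, SD, measurement error or correlation for BCVA; the only arithmetic to confirm is 3 × 20 = 60. All SDs below are assumptions, in letters.

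**1. AUC weights.** Visits are at Weeks 0, 4, 12, 24, 36 and 48. Trapezoid weights in weeks are 2, 6, 10, 12, 12 and 6, total 48. Change at Week 0 is zero, so the post-baseline weight is W = 46/48 = 0.958, with W² = 0.918. The sum of squared post-baseline weights is (36 + 100 + 144 + 144 + 36)/2304 = 0.200.

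**2. Model.** Screening = T + error; Day 1 = T + error; each follow-up = T + C + error. T is true baseline acuity (SD σT), C is a subject's true shift, present from Week 4 (SD σC), and errors are independent (SD σe). Then:

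- Unexplained variance of T given Day 1: σT²σe²/(σT² + σe²)
- Unexplained variance of T given Day 1 and Screening: σT²σe²/(2σT² + σe²)
- Residual variance of AUC = W² × (unexplained variance of T) + W²σC² + 0.200σe²

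**3. Worked case:** σT = 6, σe = 3.5, σC = 4.

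- Given Day 1: 36 × 12.25/48.25 = 9.14
- Given both: 36 × 12.25/84.25 = 5.23
- Residual with Day 1: 0.918 × 9.14 + 0.918 × 16 + 0.200 × 12.25 = 25.5
- Residual with both: 0.918 × 5.23 + 0.918 × 16 + 0.200 × 12.25 = 21.9
- Ratio: 0.86. Residual degrees of freedom fall from 56 to 55, so 0.86 × 56/55 = 0.875, a variance about 12% lower.

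**4. Same formula, other assumptions** (σT = 6, after the 56/55 factor):

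| σe | σC | Variance ratio |
|---|---|---|
| 2.5 | 4 | 0.91 |
| 3.5 | 4 | 0.88 |
| 5 | 4 | 0.86 |
| 3.5 | 2 | 0.77 |
| 3.5 | 6 | 0.94 |
| 2 | 6 | 0.98 |
| 1.5 | 8 | 1.00 |

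**5. Simulation, 3 arms × 20.** With a different assumed course of change over time, the standard errors of dose minus sham with one and with two covariates were (σT = 6):

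| σe | σC | One | Two | Variance ratio |
|---|---|---|---|---|
| 2.5 | 4 | 1.243 | 1.160 | 0.87 |
| 3.5 | 4 | 1.460 | 1.330 | 0.83 |
| 5 | 4 | 1.675 | 1.528 | 0.83 |
| 3.5 | 2 | 1.167 | 0.992 | 0.72 |
| 3.5 | 6 | 1.768 | 1.688 | 0.91 |

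The fourth row is the 28% end of the range. At the other end, truncating Screening at 69 letters with σe 1.5 to 2 and σC 6 to 8 leaves about 0% to 1.5%. A separate calculation, using the mean of the two readings and letting correlation decay over time, gives ratios of 0.99 to 0.85. Equal correlation between all visits gives 0.77 to 0.62, but it leaves no room for correlation to fall over time and is a best case only.

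**6. Two covariates or their mean?** Suppose Screening predicts less well: correlations with the outcome of 0.7 (Day 1) and 0.5 (Screening), and 0.7 between readings. One covariate leaves 1 − 0.49 = 0.51. The mean of the two has correlation 1.2/√3.4 = 0.651 with the outcome and leaves 0.576, a ratio of 1.13, which is worse. Two separate covariates give R² = (0.49 + 0.25 − 0.49)/0.51 = 0.490 and leave 0.51, a ratio of 1.00, or 1.018 after the lost degree of freedom. Separate entry therefore risks about 2% at worst.

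**The case against.** **The baseline rule is sound, and the study is descriptive.** Both are true. Taking the last pre-dose value gives a valid, unbiased baseline, and nothing here asks for it to change. Protocol 11.3.7 calls all analysis descriptive, and no decision rule depends on this standard error. This limits the importance of the point. It does not remove it, because the SAP still reports an adjusted comparison with sham.

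**The size is assumed.** This also stands. A reader might turn the middle of the range into a firm claim, such as the equivalent of 23 to 24 subjects per arm instead of 20. The documents supply none of the SDs behind such a figure, and other plausible inputs give almost nothing.

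**A reader might extend the point to the DRSS-step MMRM**, which uses "fixed effects for treatment and visit and the interaction between treatment and visit, and baseline DRSS step as a covariate" and the rule "Baseline is defined as the last non-missing DRSS measurement prior to the initiation of study treatment". The extension fails in practice. Eligibility requires "Study eye with moderately severe to severe NPDR (based on the DRSS levels 47 or 53", so the Screening grade takes only two adjacent levels and carries little extra information. Simulated variance ratios with both readings as covariates were 0.976 to 1.00, a gain of 0% to 2.4%. Nor is Screening DRSS ignored: SAP Table 14.2.17 reports improvement measured from Screening.

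**A reader might take a baseline category in SAP 9.3 as proof that the two readings are expected to differ**: "Baseline DRSS score in the study eye (43, moderate NPDR; 47, moderately severe NPDR; 53, severe NPDR". That does not follow. The same list has a BCVA stratum of 55 letters or fewer, although entry requires at least 69. The list therefore contains categories outside eligibility for reasons that need not be measurement error.

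**Implementation gaps.** Rescreening (Protocol 3.4 and 4) and a missing Day 1 value need a stated rule. This is fair, and the fix covers it.

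**Conclusion.** The point holds as a small missed efficiency in one secondary analysis. Two pre-randomization BCVA readings are scheduled, and the AUC ANCOVA uses one. Adding the other would lower the variance of each dose-minus-sham estimate by about 1% to 28% with 20 per arm. The gain is larger when measurement error is large relative to true change, and near zero when it is small. The range rests on assumed SDs and an assumed course of change over time.

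It is not an error or a source of bias, and it does not put the baseline definition in doubt. It does not affect the visible primary analysis in SAP 10.1, which is counts with Clopper-Pearson intervals; part of that section is redacted. It should not be extended to the DRSS-step model. Classification: free improvement.

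**What to change.** In the Area Under the Curve paragraph of SAP 10.2, with a matching line in SAP 8.8:

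- Keep AUC of change from the existing baseline (Day 1, or the last pre-dose value) as the outcome.
- Add Screening BCVA in the study eye as a second, separate covariate, not averaged with Day 1.
- For a rescreened subject, use the Screening visit that qualified the subject.
- If the Day 1 value is missing and Screening is itself the baseline, the same value serves for both covariates.

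Leave the DRSS-step MMRM as it is. The cost is one residual degree of freedom (56 to 55 with 60 subjects) and SAP wording. No visit, data item, endpoint definition or estimated quantity changes. The amendment should be made before any unmasked results are seen, that is, before the Week 36 readout.
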